#### 4.7.4 Vital Signs Assessments

Vital signs, including systolic and diastolic blood pressure, heart rate, and respiration rate, will be summarized using descriptive statistics by cohort and treatment group at each time point for subjects in the Safety Population. The change from BL to each post-ciraparantag/PBO dose time point will also be summarized.

Post-baseline vital signs will be defined as Clinically Notable (CN) if they meet 1) the criterion value at the given visit, or 2) meet both the criterion value and the change from baseline criterion listed in [Table 6](#). The number and percentage of subjects with at least 1 CN vital sign at any post-baseline timepoint will be summarized by cohort, treatment, and parameter. Percentages for each vital sign will be based on the number of subjects with a baseline and a post-baseline evaluation for the specific parameter.

A separate listing will be provided of subjects with values for a vital sign noted as CN.

**Table 6. Criteria for Clinically Notable Vital Signs**

Vital Sign Parameter	Criterion Value		Change from Baseline
Systolic Blood Pressure (mmHg)	High	$\geq 180$	Increase of $\geq 20$
	Low	$\leq 90$	Decrease of $\geq 20$
Diastolic Blood Pressure (mmHg)	High	$\geq 105$	Increase of $\geq 15$
	Low	$\leq 50$	Decrease of $\geq 15$
Heart Rate (bpm)	High	$\geq 120$	Increase of $\geq 15$
	Low	$\leq 50$	Decrease of $\geq 15$

bpm = beats per minute

Vital signs results will be listed for each subject, and summary statistics for vital signs and change from baseline will be displayed by treatment. A separate listing will be provided of subjects with values for a vital sign noted as CN.

#### **4.7.5 Resting 12-Lead Electrocardiogram**

A resting 12-lead electrocardiogram (ECG) will be performed at screening, Day -1, and at any time during the study if clinically indicated. Parameters assessed will include ventricular rate (beats per minute), RR interval (msec), PR interval (msec), QRS duration (msec), QT interval (msec), and QTc interval (msec), as well as any other observed abnormalities.

All ECG results will be listed.

### **4.8 Pharmacokinetic (PK) Analysis**

#### **4.8.1 Plasma and Serum Concentrations**

Individual subject plasma concentrations of ciraparantag and its primary metabolite (BAP) and each anticoagulant (apixaban or rivaroxaban) will be listed and summarized using descriptive statistics (n, arithmetic mean, standard deviation, coefficient of variation, minimum, median, maximum, geometric mean and geometric coefficient of variation) for each time point. Values below the quantification limit (BQL) will be treated as “0” in the summary statistics. Descriptive statistics that are not quantifiable will be designated as ‘NC’ in the summaries and a footnote added, NC = not calculable.

Plots of mean concentration levels of ciraparantag and its metabolite, and each anticoagulant versus time will be generated for each cohort and treatment. Plots of individual subject’s concentration levels of ciraparantag and its metabolite, and each anticoagulant versus time will also be generated.

#### **4.8.2 Pharmacokinetic Parameters**

The PK parameters will be computed using non-compartmental analysis using appropriate software and summarized using descriptive statistics. PK parameters for ciraparantag and BAP, as displayed in [Table 7](#), and key PK parameters for anticoagulants, will be listed by subject and summarized by treatment using descriptive statistics (n, arithmetic mean, standard deviation, coefficient of variation, minimum, median, maximum, geometric mean and geometric coefficient of variation).  $T_{max}$  will be described using n, minimum, median, and maximum.

The following PK parameters for ciraparantag and its metabolite, BAP, will be calculated for diagnostic purposes and listed, but will not be summarized.

**Table 7 Listing of Diagnostic Parameters for the Non-Compartmental Analysis of Serum Ciraparantag and BAP**

$T_{1/2}$ , Interval	The time interval (h) of the log-linear regression to determine $t_{1/2}$
$t_{1/2}$ , N	Number of data points included in the log-linear regression analysis
$t_{last}$	Time to the last quantifiable concentration
Rsq	Goodness-of-fit statistic for calculation of $\lambda_z$ (regression coefficient)
%AUC ex	Percentage of AUC (0-inf) that is extrapolated from $t_{last}$ to infinity, calculated as: $100 \times [1 - (AUC_{last}/AUC_{0-inf})]$ , where $t_{last}$ is the time of the last measurable plasma drug concentration

#### 4.8.3 Dose Proportionality

Dose proportionality will be examined by a comparison of the geometric means of the ciraparantag and BAP PK parameters AUC(0-inf), AUC(0-last), and Cmax between the two ciraparantag doses using the natural log-transformed values. Confidence intervals (90%) will be constructed for the geometric mean ratios using the log transformed data. The geometric mean ratios and confidence limits will be exponentiated back to the original scale. Dose proportionality will be concluded if the 90% confidence interval includes “the ratio of the doses”. For example, if the two ciraparantag doses are 180mg and 360 mg, the ratio of the two doses will be 2.

#### 4.9 Interim Analysis

Within each cohort, an initial group of subjects (Group 1) will be enrolled for evaluation of a target dose of ciraparantag (180 mg IV). Depending on the efficacy and safety results from Group 1, a second group (Group 2) may be enrolled to evaluate a different dose of ciraparantag for that cohort, as determined by a data review team. Due to the observed lack of efficacy of ciraparantag in Group 1 subjects of Cohorts 1 and 3, no patients will be enrolled for Group 2.

#### 4.10 Statistical Programming and Deliverables

All statistical analyses, tables and listings will be generated in SAS (version 9.4 or later) with appropriate documentation and programming validation. However, the p-value for

Boschloo's test will be obtained using R. The table of contents of all tables, listings, and figures will be presented in a Tables, Listings and Figures shell supplemental document.

#### **4.11 Changes from Pre-Specified Analyses**

The following changes were made to the protocol-specified efficacy analyses

- For the primary efficacy endpoint, the protocol specified that the Cochran-Mantel-Haenszel Test, with stratification by age group, will be used to compare each active dose with placebo as a sensitivity analysis. This analysis won't be performed.
- For the secondary efficacy endpoints, the protocol specified that they would be analyzed in the same manner as the primary efficacy endpoint. This has been simplified such that the first two secondary efficacy endpoints will be summarized using counts and percentages, and no statistical analysis will be performed for the remaining secondary efficacy endpoints.
- For the first four sets of tertiary efficacy endpoints, the protocol specified that they would be analyzed in the same manner as the primary efficacy endpoint. This has been simplified such that only counts and percentages will be presented.
- For the fifth and the sixth sets of tertiary efficacy endpoint, the Analysis of Covariance (ANCOVA) specified by the protocol will not be performed.
- The protocol specified that the agreement between these two methods with respect to the efficacy endpoints at 1 hour after administration of ciraparantag/PBO will be assessed, and this analysis will not be performed.

#### **4.12 Changes to the Planned Analysis**

Any deviation(s) of consequence from the SAP during the data analysis will be documented and justified in an amended SAP and/or in the final report or addressed in a separate document, as appropriate.

## Appendix 1. Clinically Notable (CN) Laboratory Criteria

Unless otherwise specified, values in this table correspond to the thresholds for Grade 3 laboratory abnormalities as presented in the U.S. FDA Toxicity Grading Scale for Healthy Adult and Adolescent Volunteers Enrolled in Preventive Vaccine Clinical Trials (2007).

Parameter		Criterion	
		Conventional Units	SI Units
Serum chemistry			
Alanine aminotransferase (ALT)		$\geq 5.1 \times \text{ULN}$	
Albumin		$< 2.5 \text{ g/dL}$	$< 25 \text{ g/L}$
Aspartate aminotransferase (AST)		$\geq 5.1 \times \text{ULN}$	
Bilirubin, Total		$\geq 2 \times \text{ULN}$	
Alkaline phosphatase (ALP)		$\geq 3.1 \times \text{ULN}$	
Blood urea nitrogen (BUN)		$> 31 \text{ mg/dL}$	$> 11.1 \text{ mmol/L}$
Calcium	Low	$\leq 7.4 \text{ mg/dL}$	$\leq 1.85 \text{ mmol/L}$
	High	$\geq 11.6 \text{ mg/dL}$	$\geq 2.9 \text{ mmol/L}$
Creatinine		$\geq 2.1 \text{ mg/dL}$	$\geq 160.1 \text{ }\mu\text{mol/L}$
Glucose	Low	$\leq 54 \text{ mg/dL}$	$\leq 3 \text{ mmol/L}$
	High	$> 200 \text{ mg/dL}$	$> 11.1 \text{ mmol/L}$
Potassium	Low	$\leq 3.2 \text{ mEq/L}$	$\leq 3.2 \text{ mmol/L}$
	High	$\geq 5.5 \text{ mEq/L}$	$\geq 5.5 \text{ mmol/L}$
Sodium	Low	$\leq 129 \text{ mEq/L}$	$\leq 129 \text{ mmol/L}$
	High	$\geq 148 \text{ mEq/L}$	$\geq 148 \text{ mmol/L}$
Hematology			
Hemoglobin, female		$\leq 9.4 \text{ g/dL}$	$\leq 94 \text{ g/L}$
Hemoglobin, male		$\leq 10.4 \text{ g/dL}$	$\leq 104 \text{ g/L}$
Platelet count		$< 100 \times 10^3/\mu\text{L}$	$< 100 \times 10^9/\text{L}$
White blood cell (WBC) count	Low	$< 1.5 \times 10^3/\mu\text{L}$	$< 1.5 \times 10^9/\text{L}$
	High	$> 20 \times 10^3/\mu\text{L}$	$> 20 \times 10^9/\text{L}$
Neutrophils		$< 1 \times 10^3/\mu\text{L}$	$< 1 \times 10^9/\text{L}$
Eosinophils a		$> 1 \times 10^3/\mu\text{L}$	$> 1 \times 10^9/\text{L}$
Eosinophils a		$> 10\%$	

ULN = upper limit of the normal range

a. Sponsor-defined clinically notable threshold for ciraparantag

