### **4.2. Exclusion Criteria**

Eligible subjects must not:

1. Have any of the following findings at Screening:
  - a. Hemoglobin or hematocrit value outside the normal range
  - b. Platelet count outside the normal range
  - c. PT or aPTT outside the normal range
  - d. Plasma fibrinogen outside the normal range
  - e. Serum triglycerides or total cholesterol outside the normal range
  - f. Serum creatinine >1.5 mg/dL (133 µmol/L) or known renal disease
  - g. Aspartate aminotransferase (AST) or alanine aminotransferase (ALT) >2 x the upper limit of normal, or known liver disease
  - h. Total bilirubin outside the normal range
  - i. Positive viral screen for hepatitis B virus, hepatitis C virus (HCV), or human immunodeficiency virus (HIV)
  - j. Positive pregnancy test (females)
  - k. Positive drug, tobacco or alcohol screen
  - l. Any clinically significant findings on 12-lead ECG or urinalysis

2. Have a personal or family history of clotting disorder or hematologic abnormality, such as excessive bleeding, joint hematoma, thrombovascular disease, thrombocytopenia, or any chronic condition requiring treatment with transfusions.
3. Have a history of unexplained syncope.
4. Have a history within 6 months prior to Screening of major bleeding, trauma, surgical procedure of any type, or vaginal delivery.
5. Have a history within 6 months prior to Screening of peptic ulcer or gastrointestinal bleeding (including hematemesis, melena, or rectal bleeding).
6. Have received any blood product or anticoagulant within 3 months prior to Screening.
7. Have donated blood or blood products within 3 months prior to Screening.
8. Have a history of minor bleeding episodes (eg, epistaxis, bruising or gingival bleeding) within 1 month prior to Screening, or a long-standing history of such bleeding.
9. If female, have a history of excessive or dysfunctional uterine bleeding (unless the subject had a subsequent hysterectomy).
10. Have used any tobacco or nicotine-containing products within 3 months prior to Screening.
11. Have used any systemic prescription or non-prescription drugs (including vitamins, supplements, and herbal products) within 14 days prior to Day 1 (except for permitted contraceptives). NOTE: subjects should be asked specifically about use of aspirin and other non-steroidal anti-inflammatory drugs.
12. If female, be pregnant, breastfeeding, or planning to become pregnant during the study.
13. Have received ciraparantag in any prior clinical study.

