#### **4.7.3 Clinical Laboratory Assessments**

All quantitative laboratory test results, including serum chemistry, hematology, and prothrombotic markers, will be summarized by cohort, treatment, parameter, and time point using descriptive statistics for subjects in the Safety Population. The change from BL to each post-ciraparantag/PBO dose time point will also be summarized. Urinalysis results will be tabulated by counts and percentages. These will also be summarized by pooled ciraparantag vs pooled PBO across cohorts.

Laboratory values will be reported in Système International units.

Clinically notable (CN) laboratory values will be determined based on the criteria in [Appendix 1](#). The number and percentage of subjects with at least 1 CN laboratory value at any post-baseline timepoint will be summarized by cohort, treatment, and parameter.

Percentages for each laboratory test will be based on the number of subjects with at least one post-baseline evaluation for the specific parameter.

In addition to the CN summary, the number and percentage of subjects meeting each of the following criteria at any post-baseline timepoint will be summarized by cohort, treatment, and parameter:

- AST >3 x ULN, >5 x ULN and >10 x ULN
- ALT >3 x ULN, >5 x ULN and >10 x ULN
- Total bilirubin >1.5 x ULN and >2 x ULN

Laboratory values will be listed for each subject. Laboratory values outside normal limits will be identified in the subject data listings with flags for low (L) and high (H) as will laboratory values that meet the CN thresholds. A separate listing will be provided of subjects with values for a laboratory parameter noted as CN.

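### SAP Appendix 1: the two cut-offs for clinically notable creatinine, 2.1 mg/dL and 160.1 µmol/L, are not the same concentration

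*SAP*

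**What the plan says.** SAP Appendix 1 lists the CN laboratory criteria in two columns, conventional and SI. For creatinine the conventional cell is at least 2.1 mg/dL and the SI cell is "\geq 160.1 \text{ }\mu\text{mol/L", that is, at least 160.1 µmol/L. The lead-in states that, unless marked otherwise, "values in this table correspond to the thresholds for Grade 3 laboratory abnormalities" in a cited toxicity grading scale. The creatinine row carries no footnote marking it as an exception.

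SAP 4.7.3 puts the table to use. "Clinically notable (CN) laboratory values will be determined based on the criteria in" Appendix 1, and "The number and percentage of subjects with at least 1 CN laboratory value at any post-baseline timepoint will be summarized by cohort, treatment, and parameter". CN values are also flagged in the subject listings and shown in a separate listing. The same section says "Laboratory values will be reported in Système International units". It does not say which column of Appendix 1 the flag uses.

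The protocol gives its own creatinine conversion in exclusion criterion 1f (Section 4.2 and the Synopsis): "Serum creatinine >1.5 mg/dL (133 µmol/L) or known renal disease".

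**The concern.** A two-column threshold table works only if both columns describe the same threshold. For creatinine they do not, so the classification of a result depends on the unit system used when the flag is derived. Two programmers could follow the same SAP and produce different CN tables.

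The groups are small. The randomization target is 12 ciraparantag and 6 placebo subjects per group, and the CN summary is by cohort and treatment. With full evaluable groups, one reclassified subject moves a cell by 1/12 = 8.3 or 1/6 = 16.7 percentage points.

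**Working it through.** **Inputs**
- CN creatinine, conventional: 2.1 mg/dL (SAP Appendix 1).
- CN creatinine, SI: 160.1 µmol/L (SAP Appendix 1).
- The documents' own conversion: 1.5 mg/dL = 133 µmol/L (Protocol 4.2, criterion 1f).
- Molar mass of creatinine: 113.12 g/mol. This is a standard constant that is not in the documents. It serves only as a cross-check.

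**1. Can the SAP's pair be reproduced?** The factor it implies is 160.1 / 2.1 = 76.2 µmol/L per mg/dL. The protocol's factor is 133 / 1.5 = 88.67, and the molar-mass factor is 10000 / 113.12 = 88.40. The last two agree: 1.5 × 88.40 = 132.6, which rounds to the protocol's 133. The SAP's pair fits neither.

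**2. Convert 2.1 mg/dL to SI.**
- Protocol factor: 2.1 × 88.67 = 186.2 µmol/L. If 133 stands for anything from 132.5 to 133.5, the result is 185.5 to 186.9.
- Molar mass: 2.1 × 88.40 = 185.6 µmol/L.

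**3. Convert 160.1 µmol/L back.** 160.1 / 88.67 = 1.81 mg/dL; 160.1 / 88.40 = 1.81 mg/dL.

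**4. Size of the gap.**
- Molar mass: 185.6 − 160.1 = 25.5 µmol/L, or 13.8% of 185.6.
- Protocol factor: 186.2 − 160.1 = 26.1 µmol/L, or 14.0% of 186.2.

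**5. Could rounding explain it?** If 2.1 stands for anything from 2.05 to 2.15 mg/dL, the molar-mass factor gives 181.2 to 190.1 µmol/L. The value 160.1 lies well outside.

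**6. Do the other rows convert?** The rows that need a molar conversion, using standard molar masses:

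| Row | Conventional (mg/dL) | Converted (mmol/L) | SAP SI cell (mmol/L) |
|---|---|---|---|
| BUN | 31 | 11.07 | 11.1 |
| Calcium, low | 7.4 | 1.85 | 1.85 |
| Calcium, high | 11.6 | 2.89 | 2.9 |
| Glucose, low | 54 | 3.00 | 3 |
| Glucose, high | 200 | 11.10 | 11.1 |

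Albumin and hemoglobin (× 10), potassium and sodium (mEq/L = mmol/L) and the cell counts also agree. Creatinine is the only mismatched row, so a different convention across the table is not the explanation.

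**7. Results affected.** Values from 160.1 to just under about 186 µmol/L (about 1.81 to just under 2.1 mg/dL) are CN by the SI column and not CN by the conventional column.

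**The case against.** The mismatch itself has no good defence; nothing in either document corrects it. The case on the other side concerns how far the point reaches, and much of that stands.

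- **Which column is used.** A reader might infer that, because results are reported in SI units, the 160.1 cut-off is certain to be applied. SAP 4.7.3 does not say so. It states the reporting units and, separately, that CN status follows a table with both columns. Chemistry is tested at local laboratories (Protocol 6.6), and the documents do not give the units in which results arrive, so the flag could be derived before or after conversion. Use of the SI column is a reasonable inference and no more.
- **Which cell is wrong.** A reader might also infer that 2.1 mg/dL is right, so that 160.1 is too low and over-flags. The arithmetic shows only that the cells conflict. The appendix defers to a grading scale that is not in the documents. If 160.1 µmol/L were the intended value and the conventional column were programmed, the error would run the other way and miss values.
- **How many results could be affected.** Subjects are healthy volunteers whose screening creatinine is no higher than 1.5 mg/dL. To reach the disputed band, a value must rise at least 20% above that ceiling (160.1 / 133 = 1.20). The study was terminated, and only Group 1 of Cohorts 1 and 3 is analysed, with a target of 2 × 18 = 36 subjects. Scheduled chemistry after dosing is at FU-1 and FU-5 only. Few or no results in the band is plausible, and the documents allow no estimate.
- **What remains visible.** All laboratory values are listed with high and low flags, and quantitative results and changes from baseline are summarised. No result is hidden by a misplaced CN cut-off.

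These points limit the consequence. They do not remove the contradiction in a prespecified criterion.

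**Conclusion.** The point holds as an internal contradiction. The two creatinine cells in SAP Appendix 1 differ by about 25.5 µmol/L (13.8%), and any result from 160.1 to just under about 186 µmol/L is classified differently by column. This rests on the protocol's own conversion alone; the molar mass only confirms it.

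Neither the intended cell nor the programmed column can be settled from the documents. The effect is confined to the CN creatinine count, flags and listing, which are descriptive. Efficacy analyses do not use the threshold. Eligibility uses 1.5 mg/dL, and the listed enrolment stopping criteria (Protocol 10.2.3) name bleeding, serious adverse events, transaminases and bilirubin, not creatinine. It is a small correction that is worth making.

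**What to change.** 1. Check the creatinine row against the cited Grade 3 source and make the columns agree. If 2.1 mg/dL stands, the SI cell becomes about 186 µmol/L. If 160.1 µmol/L stands, the conventional cell becomes about 1.81 mg/dL. Fix the SI value to a stated precision and factor, because 185.6 and 186 are different cut-offs under an at-least rule.
2. Add one sentence to SAP 4.7.3 naming the column that drives the CN flag.
3. Produce the CN creatinine count, listing flags and separate listing from the reconciled value. If any of these outputs already exist, regenerate them.

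The cost is one table cell, one sentence and one value in the flagging program. No new data are needed and no other analysis changes.

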**Revision history**

Version	Date	Comments
